## 1 INTRODUCTION

Obsessive compulsive disorder (OCD) affects 1–2% of children and adolescents, and is characterized by the presence of recurrent, unwanted thoughts (obsessions) and repetitive behaviors (compulsions) that create psychological distress and impair daily activities at home, at school, and with peers [4]. An unknown proportion of pediatric OCD cases have features related to two putative OCD subtypes: pediatric acute-onset neuropsychiatric syndrome (PANS) and/or pediatric autoimmune neuropsychiatric disorders associated with streptococcal infection (PANDAS).

The first description of PANDAS, published in 1998, defined it as the sudden onset of obsessive-compulsive or tic disorder symptoms following a GAS infection [5]. In a clinical setting, PANDAS is observed as a cluster of abrupt onset symptoms following a GAS infection, including a pathogenic flare with severe obsessive compulsions (e.g. shoe licking) and/or tics (e.g. whooping), and concomitant symptoms, including developmental (behavioral) regression marked in separation anxiety and aggression [1, 6]. Due, in part, to the challenge of determining temporal association between GAS infection and the onset of OCD and/or tic symptoms, relatively few PANDAS cases have been confirmed through these strict criteria [7]. Thus, the validity of PANDAS as a unique clinical entity has been brought into question, becoming a topic of significant debate and controversy among psychiatrists and neurologists [8]. In an effort to resolve this debate, a new diagnostic syndrome was proposed in 2012. Termed PANS, this new definition addressed the primary criticism of the PANDAS definition by eliminating the requirement of a preceding GAS infection [9]. Hereafter, in the context of this clinical study protocol, any mention of PANS also includes a minority of patients with PANDAS.

Cognitive behavior therapy (CBT) including exposure and response prevention, and selective serotonin re-uptake inhibitors (SSRIs) are the primary evidence-based therapies for OCD [10, 11]. Approximately 50%–80% of patients with OCD respond to these treatments, but a substantial proportion of patients subsequently experience lifelong treatment resistance [12]. Behavioral interventions, such as habit reversal training, and psychopharmacological treatment strategies are the recommended treatments for tic disorders [13]. In contrast to the recommended treatments, when an infectious or autoimmune etiology is suspected, these treatments for OCD and tics may be insufficient.

Supplemental or alternative treatment options when suspecting PANDAS include antibiotics or tonsillectomy to treat and/or prevent GAS infection [14]. To suppress the immune system in patients with putative autoimmune-based OCD, corticosteroids [15], therapeutic plasma exchange [16, 17], IVIG [17], or anti-CD20 monoclonal antibodies (rituximab) [15] have been given. Administration of non-steroidal anti-inflammatory drugs (NSAIDs) to ameliorate psychiatric symptoms of PANS also has been suggested and is in line with the autoimmune etiology theory [18]. A consortium of clinicians and researchers have authored three consensus papers regarding treatment of PANS using psychiatric and behavioral interventions [19], immunomodulatory therapies [20], and antibiotics [21]. These guidelines of the clinical management of PANS are based on clinical experience and on research, and support use of immunomodulatory treatment and antibiotics, beside standard psychiatric treatment. A

systematic review on the management of PANS and related disorders identified 12 studies involving the following treatments: penicillin, azithromycin, IVIG, plasma exchange, tonsillectomy, CBT, NSAIDs, and corticosteroids [12]. A further 65 case reports in which patients received immunomodulatory treatments, antibiotics, and/or psychotropics were identified [12]. Research on PANS treatment (and related disorders) is scarce, and further investigation is needed in which treatment strategies are rigorously investigated.

As mentioned above, immunoglobulins have been used in the treatment of PANS. Panzyga is a 10% human normal immunoglobulin solution ready for intravenous administration (IVIG) developed by Octapharma. It is supplied as a ready-to-use liquid formulation. The Panzyga manufacturing process achieves significant viral reduction through a combination of [REDACTED] dedicated virus inactivation/removal steps. Adverse drug reactions (ADRs) reported for Panzyga were similar in type and intensity to those reported with other IVIG preparations. Panzyga is currently registered in [REDACTED] countries, with the first marketing authorization granted in Germany in February 2016 [22].

## 1.1 Rationale for Conducting the Study

Accumulating evidence supports conceptualizing PANS as an immune-mediated brain disease, akin to Sydenham chorea (SC) and PANDAS, involving the caudate, putamen, and other basal ganglia structures [20]. Evidence that the onset of PANS is driven by inflammation is based on animal models from a number of different research groups [23], clinical data showing overlap between PANS and other inflammatory diseases [4, 24], imaging studies [25, 26], and other research suggesting a link between inflammation and obsessive-compulsive symptoms [27-32]. Increased rates of arthritis and autoimmune/inflammatory disorders have been reported among patients with PANS and their first-degree relatives, with more than 70% of families having at least one affected family member [23, 33]. There is also emerging clinical literature reporting response of PANS symptoms to therapies, including NSAIDs, oral and intravenous corticosteroids, IVIG, and plasmapheresis [20, 34, 35]. In a retrospective review of patients in the Stanford PANS-PANDAS clinic, symptomatic improvement in neuropsychiatric symptoms became evident in roughly one-third of NSAIDs treatment trials [35]. Similarly, children with more severe symptoms treated with oral corticosteroids were found to have shorter exacerbations and longer periods of remission than children not receiving steroid treatment [34]. Provisional data demonstrate a positive impact of IVIG treatment in PANS patients on psychometric parameters [36].

Although the use of IVIG in the treatment of PANS/PANDAS has received considerable attention in the past decade, no additional placebo-controlled trials were published until 2016. A placebo-controlled trial of IVIG was undertaken at the National Institute of Mental Health and the Yale Child Study Center. Thirty-five children meeting criteria for PANDAS and moderate-to-severe OCD were randomized in double-blind, placebo-controlled 6-week trial of IVIG (1 g/kg body weight [BW] on two consecutive days; total dose 2 g/kg BW) [37]. Non-responders were offered open-label treatment with IVIG at six weeks, and follow-up evaluations for all participants occurred at 12 and 24 weeks. The primary outcome measures were the CY-BOCS and the CGI improvement (CGI-I) rating. “Responders” were defined, a priori, by a >30% decrease in CY-BOCS total score, and “much” or “very much” improved on CGI-I. IVIG was

safe and generally well-tolerated. The mean decrease in CY-BOCS score during the double-blind phase was  $24\pm31\%$  in the IVIG group (n=17) and  $12\pm27\%$  in the placebo group (n=18). This difference was not statistically significant (effect size = 0.28, 95% confidence interval - 0.39–0.95), with six responders in the IVIG group (35%) and four responders in the placebo group (22%). Notably, the blinded phase included only one treatment cycle, which might not be enough to show a full effect of treatment and detect a difference between IVIG and placebo. Twenty-four children met criteria for non-response and received open-label treatment (n=10 IVIG, n=14 placebo). Across all participants, a mean CY-BOCS improvement from baseline at week 12 of  $55\pm33\%$  was observed [37]. A number of unanticipated events (multiple patients acquired new GAS infections during the trial), as well as study design issues, may have decreased the effect size of the trial. Further to the above-mentioned reason, in particular, participants may also have over-reported symptom severity in the double-blind portion of the study to increase the possibility of getting open-label IVIG at six weeks.

Since there are scarce data from rigorously designed double-blind controlled trials with IVIG, Octapharma plans to assess the efficacy and safety of Panzyga treatment compared with placebo in PANS patients.

This study will be conducted in accordance with the ethical principles laid down in the Declaration of Helsinki. The study protocol and any subsequent amendment(s) will be submitted to an Independent Ethics Committee (IEC)/Institutional Review Board (IRB) and to the Regulatory Authority. The study will be conducted in compliance with the protocol, good clinical practice (GCP) guidelines, and applicable regulatory requirements.

## 1.2 Dose Rationale

According to published literature, patients with PANS respond to IVIG doses of 2 g/kg BW (divided over two consecutive days) [17, 37]. Initial high dose induction IVIG treatment (one to six monthly courses) for moderate-to-severe PANS is recommended by the guidelines adopted by PANS Research Consortium [20]. This induction dose is equivalent to that used for other pediatric inflammatory disorders, including, but not limited to autoimmune encephalitis, Kawasaki disease, juvenile dermatomyositis, idiopathic thrombocytopenic purpura, and Guillain-Barre syndrome [38, 39]. Additionally the dose of 2 g/kg BW was used in another randomized controlled study that can be regarded as a reference study in terms of IVIG dose regimen [37].

Efficacy and safety of high-dose IVIG induction treatment was shown in a multicenter, phase I/II blinded-withdrawal study with stratified entry in 25 polyarticular juvenile rheumatoid arthritis (poly-JRA) patients. Similar to PANS, autoimmune inflammation is the underlying pathophysiologic disease mechanism in poly-JRA. In this pediatric study, IVIG was given in a dose of 1.5–2.0 g/kg BW bimonthly for two months (up to a total dose of 8 g/kg over eight weeks) followed by monthly infusions [40].

Patients in the Panzyga arm will, therefore, receive 1 g/kg BW daily for two consecutive days, if tolerated, administered in three-week intervals up to nine weeks (total Panzyga exposure: 6 g/kg BW).

### 1.3 Benefit-Risk Statement

Risks associated with assignment to the placebo arm include adverse events (AEs) or worsening of symptoms. At this time, no data from pediatric PANS/PANDAS or OCD clinical trials suggest a risk of permanent worsening of symptoms or long-term outcome in children assigned to a placebo arm up to nine weeks' duration. The delay in access to active treatment is similar to what might be experienced by patients waiting for a clinician appointment and insurance authorization for treatment with IVIG in the community.

The risks of IVIG administration are well documented. In general, the incidence of AEs associated with IVIG tends to increase with the rate of infusions, and thus the recommended dosage, infusion rates, and monitoring procedures should be adhered to. Patients who are naïve to IVIG are more at risk than those who are well maintained and on regular therapy. In clinical studies with Panzyga, most ADRs observed in children were graded as mild, and many of them responded to simple measures, such as reduction of the infusion rate or temporary discontinuation of the infusion. With respect to the type of ADR, all were recognized for IVIG preparations. The most frequent ADR observed in the pediatric population was headache [22, 41].

The safety profile of IVIG is well characterized and, in general, the same type of adverse reactions may be expected for Panzyga. No new or unknown safety problems are expected to emerge, which are not already described in the Investigator's Brochure (IB) [22]. In general, adverse reactions such as headache, dizziness, vomiting, allergic reactions, chills, back pain, arthralgia, fever, low blood pressure and nausea may occasionally occur.

The safety profile of Panzyga is satisfactory and the number of ADRs are below the levels recommended by the US Food and Drug Administration (FDA) for products of this class. Efficacy and safety data with Panzyga are available from three clinical studies in 51 patients (including pediatric patients) with primary immunodeficiency and in 40 patients with immune thrombocytopenia [22].

The expected clinical benefit of using Panzyga in this study is improvement of neuropsychiatric symptomatology and behavior in PANS patients. IVIGs are recommended by the PANS Research Consortium for the treatment of moderate to severe PANS. A recent open label study showed statistically significant improvements in psychometric assessments from baseline after six infusions every three weeks in pediatric patients with PANS.

The main known risks of IVIG administration are listed below

- Thrombosis and thromboembolic events (TEEs) such as myocardial infarction, stroke, pulmonary embolism and deep vein thrombosis may occur with IVIG products, including Panzyga. Risk factors may include advanced age, prolonged immobilization, hypercoagulable conditions, history of venous or arterial thrombosis, use of estrogens, indwelling vascular catheters, hyperviscosity, and cardiovascular risk factors.
- Renal dysfunction, acute renal failure, osmotic nephropathy, and death may occur with the administration of IVIG products in predisposed patients (e.g. pre-existing renal insufficiency, diabetes mellitus, hypovolemia, overweight, concomitant nephrotoxic medicinal products or age over 65 years). Renal dysfunction and acute renal failure occur

more commonly in patients receiving IVIG products containing sucrose. Panzyga does not contain sucrose.

- Standard measures are taken to prevent infections resulting from the use of medicinal products prepared from human blood or plasma. Despite this, when medicinal products prepared from human blood or plasma are administered, the possibility of transmitting infective agents cannot be totally excluded. During the manufacturing process of Panzyga, significant viral reduction is obtained.
- Reversible hemolytic reactions have been observed in patients, especially those with blood groups A, B, and AB. Rarely, hemolytic anemia requiring transfusion may develop after high dose IVIG treatment.
- Aseptic meningitis syndrome is a rare but known adverse reaction that has been reported to occur infrequently in association with IVIG treatment.

Inclusion and exclusion criteria, recommendations on the rate of infusion, dosage, and monitoring procedures provided in this protocol sufficiently mitigate above-mentioned risks and must be adhered to. No new or unknown safety problems are expected to emerge in pediatric PANS population, which are not listed above or described in the IB.

Based on available data, we postulate that PANS treatment with Panzyga outweighs potential disadvantages.

## 2 STUDY OBJECTIVES

### 2.1 Primary Objective

The primary objective of this study is to confirm that Panzyga is superior to placebo (0.9% w/v sodium chloride) for reducing the severity of symptoms associated with PANS in pediatric patients who meet PANS clinical criteria.

### 2.2 Secondary Objectives

The secondary objectives of this study are to:

- verify the sustainability of the reduction of the severity of symptoms in pediatric patients treated with Panzyga.
- assess the efficacy of Panzyga treatment in reducing functional impairment associated with PANS.

### 2.3 Exploratory Objectives

The exploratory objectives of this study are to:

- assess the safety parameters of Panzyga administration.
- characterize the pharmacokinetic (PK) exposure throughout the treatment course.

Additional exploratory objectives of this study are to:

- assess the correlation between CGI-I and CY-BOCS
- assess the PANS improvement in pediatric patients

### 3 INVESTIGATIONAL PLAN

#### 3.1 Primary and Secondary Endpoints

##### 3.1.1 Primary Endpoint

Improvement of neuropsychiatric symptomatology and behavior in PANS patients determined by clinician-rated CY-BOCS score. The mean changes in the total CY-BOCS score from Baseline to Week 9 will be compared between Panzyga and placebo treatment to demonstrate superiority.

##### 3.1.2 Secondary Endpoint

- To assess behavioral changes by means of the following standardized assessments:
  - CY-BOCS score at the end of the follow-up period at Week 18 will be compared to the Week 9 scores within the (Panzyga – Placebo) treatment sequence group to assess the durability of the clinical benefit associated with Panzyga treatment
  - Clinical Global Impression (CGI)
  - Parent & Child OC Impact Scale – Revised (COIS-RP and COIS-RC)
  - SNAP-IV 26 item Scale
  - Parent Tic Questionnaire (PTQ)

##### 3.1.3 Exploratory Endpoints

- All AEs throughout the study period, with particular emphasis on TEEs and HTRs.
- Vital signs (blood pressure, heart rate, body temperature and respiratory rate).
- Physical examination at Baseline, and targeted physical examinations at Week 3, Week 6, Week 9/Early Termination Visits.
- Laboratory parameters (hematology, clinical chemistry) at Baseline and Week 9/Early Termination Visits.
- Columbia Suicide Severity Rating Scale (C-SSRS)
- Pharmacokinetic parameters related to IgG sampling (Table 3):
  - Prior to start of the first infusion of each of the three infusion cycles, i.e. three trough levels per patient in all patients
  - 10 to 60 minutes after the end of the last infusion cycle in all patients
  - In the PK-subset (first six enrolled patients), in addition to the samples above, the following three samples were collected:
    - (i) a trough sample prior to the second infusion of the first cycle;
    - (ii) a sample within 10 to 60 minutes after the end of the first infusion of the first cycle;

- (iii) a sample within 10 to 60 minutes after the end of the second infusion of the first cycle
- Correlations between change in CY-BOCS from baseline to Week 9 (from Week 9 to Week 18) and CGI-I assessments at Week 9 (Week 18)
- Percentage of pediatric patients with PANS improvement at Week 9 and Week 18. For this analysis, PANS improvement is defined as a CGI-I rating of 1 (Very much Improved), 2 (Much improved), or 3 (Minimally Improved).

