### 3.2 Overall Study Design and Plan

The study is planned to start in Q3 2021 and to be clinically completed by Q4 2024. The study will be a prospective, multicenter, randomized, double-blind, parallel group, placebo-controlled, Phase III superiority study in a minimum of █ pediatric patients with confirmed diagnosis of moderate to severe PANS with prominent and stable OCD symptoms (i.e. CGI—Severity-OCD rating of  $\geq 4$  or higher on 2 ratings without a change of more than 1 unit between measurements). The study includes an additional double-blind, crossover safety and efficacy follow-up phase of three infusions of Panzyga or placebo administered over 2 days every three weeks for a total of nine weeks.

[figure not shown]
After the first █ patients had been enrolled, the study enrollment was put on hold to further enhance the safety monitoring of Panzyga administration. The study resumed only after the Independent Data Monitoring Committee (IDMC) had reviewed unblinded safety and PK data of these █ patients and given the green light to pursue the study.

Up to 30 sites are projected to participate in this clinical study.

Eligible patients will be randomized 1:1 to two possible treatment sequences:

- (Panzyga – Placebo): three administration cycles with Panzyga, followed by three administration cycles with placebo
- (Placebo – Panzyga): three administration cycles with placebo, followed by three administration cycles with Panzyga

Patients will undergo repeated efficacy and safety assessments relating to each cycle. After completion of the first double-blind treatment period, blinded crossover assignment will be done; patients previously in the Panzyga arm will be assigned placebo and patients previously in the placebo arm will be assigned Panzyga, administered at the same regimen. Figure 1 depicts the study design. Rescreening is allowed for patients who were eligible based on the onset of symptoms, but have recently initiated CBT, psychotropic medication, corticosteroids, anti-virals, or antibiotics, provided these treatments are completed within the timelines stated in the exclusion criteria (Section 4.1.2).

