## 4.3 Withdrawal and Replacement of Patients

### 4.3.1 Premature Patient Withdrawal from the Study

Patients have the right to withdraw from the study at any time for any reason, without the need to justify their decision. The investigator also has the right to withdraw patients in case of AEs, poor compliance, or other reasons. Since an excessive rate of withdrawals can render the study non-interpretable, any unnecessary withdrawal of patients should be avoided.

For any withdrawals after study entry, the investigator will obtain all the required details and document the reason(s) for discontinuation in the eCRF. If the reason for withdrawal of a patient is an AE, the main specific event or laboratory test will be recorded in the eCRF, and the investigator will make thorough efforts to clearly document the outcome.

Patients who terminate the study prematurely are considered drop-outs. The investigator will schedule an Early Termination Visit, which is identical to the Week 18 Visit procedures.

Other reasons for premature termination of patients may be:

- Withdrawal of patient's consent.
- Pregnant and lactating patients will be immediately excluded from the study.
- Investigator's opinion that the patient may be severely harmed if he/she continues study participation, namely by the treatment and procedures requested by the study protocol.
- Patients do not comply with the study protocol.

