The effect of passive transmission of blood group antibodies will be evaluated by searching for hemolysis and performing a direct antiglobulin test (direct Coombs' test). In addition, routine hematology and serum chemistry tests will be obtained at Baseline and at the Week 9/Early Termination Visit.

Property of Octapharma. Do not copy or distribute without written permission.

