8.4. Derived and Computed Variables

The following derived/computed variables have been initially identified as important for the analysis of the primary and secondary target variables. It is expected that additional variables and flags will be required. The SAP will not be amended for additional variables that are not related to the primary target or key secondary target variables. Any additional derived or computed variables will be identified and documented in the SAS programs that create the analysis files. If the SAP is not amended, further derivations related to primary and secondary target variables will be described in the CSR.

- The age of a patient is defined according to the usual definition that a person is n years old until she or he has completed her or his (n+1)th year of life, using the date of informed consent as the reference date. This is also the definition that will be applied for evaluation of the age related inclusion criteria. [Unit: years]
- Body Mass Index: $BMI = (\text{Body weight}) / \text{Height}^2$ [Unit: kg/m^2]
- Treatment group for safety analyses: Because of the cross-over follow-up phase in this study, safety data will be summarized in 3 groups:
 1. 'Panzyga': Patients with either
 - Panzyga as the first IMP administered, from start of treatment and up to 21 days after the end of the last Panzyga infusion, or with
 - Panzyga as their 2nd treatment, from start of Panzyga treatment until the end of the observation period.
 2. 'Placebo': Patients with Placebo as their first IMP administered, from start of treatment until the first administration of Panzyga.
 3. 'Placebo after Panzyga': Patients who received Panzyga in the first period and are now treated with Placebo, from 22 days after the last Panzyga administration until the end of the observation period.

Derivations with respect to evaluation/scoring of the standardized assessment tools/questionnaires used in this study (CY-BOCS, CGI, COIS, SNAP-IV, PTQ, C-SSRS) will be done according to the respective scoring manuals and are therefore not detailed in this SAP.

Property of Octapharma. Do not copy or distribute without written permission.

9. Study Patients and Demographics

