11.2. Clinical Laboratory Evaluations

All laboratory data will be converted to standard units during the Data Management process. The laboratory data will be listed with suitable flags indicating abnormal values (L=Lower than reference range, H=Higher than reference range).

Summary statistics for the laboratory values as well as their changes from baseline will be tabulated for all laboratory parameters. The tables on changes in lab parameters will again feature columns for each treatment group as defined above and a total column in a side-by-side fashion.

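### The laboratory and physical-examination endpoints are defined only to Week 9/Early Termination, but the SAP tabulates laboratory change for safety groups that run past Week 9

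*Protocol*

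**What the plan says.** **Endpoint timing.** Protocol 3.1.3 lists "Laboratory parameters (hematology, clinical chemistry) at Baseline and Week 9/Early Termination Visits" and "Physical examination at Baseline, and targeted physical examinations at Week 3, Week 6, Week 9/Early Termination Visits". Protocol 7.5 gives the laboratory timing again: "routine hematology and serum chemistry tests will be obtained at Baseline and at the Week 9/Early Termination Visit". The synopsis and SAP 3.2.3 list the same endpoints without time points.

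**Exposure.** Protocol 3.2 states that "Eligible patients will be randomized 1:1 to two possible treatment sequences". One sequence has three Panzyga cycles and then three placebo cycles; the other has the reverse order. SAP 4.1 places the switch after Week 9, with no wash-out.

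**Safety groups.** SAP 8.4 defines three:
- *Panzyga* covers Panzyga-first patients up to 21 days after their last Panzyga infusion. It also covers patients with "Panzyga as their 2nd treatment, from start of Panzyga treatment until the end of the observation period".
- *Placebo* covers placebo-first patients until their first Panzyga.
- *Placebo after Panzyga* starts 22 days after the last Panzyga administration.

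**Laboratory tables.** SAP 11.2 summarizes values and changes from baseline, and adds: "The tables on changes in lab parameters will again feature columns for each treatment group as defined above". SAP 4.3 equates Baseline with Week 0. Neither SAP 8.4 nor SAP 11.2 gives a different reference value for patients who switch to Panzyga.

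**Early termination.** Protocol 4.3.1 provides for an "Early Termination Visit, which is identical to the Week 18 Visit procedures".

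**The concern.** An endpoint definition says which data belong to the endpoint. Here two protocol sections close the laboratory endpoint at the visit where the Placebo–Panzyga sequence is about to start Panzyga. The SAP then builds laboratory columns that need values from after that visit. A programmer who follows the protocol text would have nothing on Panzyga from that sequence's completers. One who follows the SAP would use values that the endpoint definition does not mention.

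There is a second question, which remains however the first is settled. If a later laboratory value exists for a Placebo–Panzyga patient, the SAP's change from baseline runs from Week 0. That change covers the whole placebo phase as well as the Panzyga phase, yet it would appear in the Panzyga column.

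What is at stake is the clarity of the laboratory safety tables. Protocol 1.3 names renal dysfunction and hemolysis among the known risks of IVIG, so these tables will be read with attention.

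**Working it through.** The plan gives no figure to reproduce. The check compares visit timing with the SAP windows, using only the nominal schedule.

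**Step 1: nominal days.** Take the first infusion as Day 0, with cycles every three weeks and two consecutive infusion days per cycle.
- Last Panzyga infusion in the Panzyga–Placebo sequence: second day of the Week 6 cycle, 6 × 7 + 1 = Day 43.
- Week 9: 9 × 7 = Day 63.
- Gap: 63 − 43 = 20 days.
- End of the SAP's Panzyga window: 43 + 21 = Day 64.
- Start of *Placebo after Panzyga*: 43 + 22 = Day 65.

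**Step 2: which SAP columns receive a value if the endpoint is as worded in Protocol 3.1.3 and 7.5?**

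| SAP 8.4 group | Patients and period | Laboratory value named in 3.1.3 and 7.5 |
|---|---|---|
| *Panzyga* | Panzyga–Placebo, to Day 64 | Week 9 (Day 63) |
| *Panzyga* | Placebo–Panzyga, from first Panzyga onward | None for completers |
| *Placebo* | Placebo–Panzyga, before first Panzyga | Week 9, if drawn before the infusion |
| *Placebo after Panzyga* | Panzyga–Placebo, from Day 65 | None for completers |

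Two of the four rows are empty for completers. A patient who terminates early in the second phase would supply a value. The last row depends on timing: a Week 9 sample taken at least 65 − 63 = 2 days late would move into *Placebo after Panzyga*. The allowed visit windows are not visible.

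**Step 3: does the visible text agree with itself?** Protocol 3.1.3 and 7.5 put laboratory tests at the Early Termination Visit. Protocol 4.3.1 makes that visit the same as Week 18. If both are right, Week 18 has laboratory tests and the endpoint wording is incomplete. If Week 18 has none, the statement in 4.3.1 does not fit 3.1.3 and 7.5. Reconciliation is needed in either case, and this does not depend on the blacked-out flow charts.

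**Step 4: the reference value.** Write Y0, Y9 and Y18 for a Placebo–Panzyga patient's laboratory value at Weeks 0, 9 and 18. Y18 is assumed to exist. Then

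Y18 − Y0 = (Y9 − Y0) + (Y18 − Y9).

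The first term is change over nine weeks on placebo and the second is change over nine weeks on Panzyga. With Week 0 as the reference, the first term enters the *Panzyga* column, although the same quantity is already this patient's entry in the *Placebo* column. With Week 9 as the reference, only the second term remains.

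**The case against.** The strongest reply is that the plan very probably does collect these data. Besides Protocol 4.3.1, several visible passages point that way:
- Section 6 requires investigators to review laboratory results from the preceding visit before each new infusion cycle, with no exception for the second phase.
- Protocol 4.3.2 says that safety laboratory tests linked to IMP administration are omitted once study drug stops. That ties them to dosing, and dosing continues through the sixth cycle.
- Protocol 7.3.5.2 has hemolytic reactions monitored at every visit.
- The synopsis has safety data collected at Week 18.
- SAP 11.5 has physical examinations throughout the study.

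Protocol 7.3.6 defers laboratory timing to Section 6, whose visit detail is blacked out, as are the flow charts. What is blacked out cannot be treated as missing.

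This reply stands, and it rules out the stronger reading. A reader might infer that laboratory safety would be judged on only half of the exposed children: with 1:1 allocation and full adherence, 3 × N/2 of the 3 × N scheduled Panzyga cycles fall after the Week 9 assessment. The documents do not support that inference. It needs an absence of later tests, which the visible text does not show and largely contradicts. Nor can a loss of precision be calculated, because the sample size is blacked out.

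Two further points count against a large effect. Adverse events, including abnormal laboratory findings, are collected to the end of the study (Protocol 7.3.2). Targeted physical examinations are limited to conditions identified at Screening (Protocol 7.1.3 and 7.3.8), so the physical-examination part adds little.

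The reply does not remove the mismatch. If tests run to Week 18, Protocol 3.1.3 and 7.5 describe an endpoint that leaves them out. It also does not address the reference value.

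**Conclusion.** The point holds as an inconsistency between the endpoint definition and the analysis. Protocol 3.1.3 and 7.5 stop the laboratory endpoint, and 3.1.3 the physical-examination endpoint, before the Placebo–Panzyga sequence has any Panzyga. SAP 8.4 and 11.2 need laboratory values from after that point for part of the *Panzyga* column and for the *Placebo after Panzyga* column. Omission of tests is not shown.

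Severity is minor. The endpoints are exploratory and the repair is mostly wording. The one substantive element is the reference value: for Placebo–Panzyga patients, a change from Week 0 attributes nine weeks of placebo time to Panzyga.

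The conclusion assumes nominal visit timing for the 20-day gap, a Week 9 sample drawn before the first second-phase infusion, and completion of the second phase.

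**What to change.** 1. Reconcile Protocol 3.1.3 and 7.5 with the synopsis, Protocol 4.3.1 and Section 6, and with SAP 8.4, 11.2 and 11.5, so that second-phase laboratory and physical-examination data already scheduled fall within the endpoint. Which visits carry which tests is for the sponsor to state; no added test is proposed here.
2. In SAP 11.2, state the reference value for each safety group. For Placebo–Panzyga patients, report on-Panzyga laboratory change from the Week 9 value taken before the first Panzyga infusion. Change from Week 0 can be kept alongside it.

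The first item costs wording only. The second costs one derived reference value and one extra table. Neither adds a procedure for patients.
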